9.5. Efficacy Analysis

9.5.1. Primary Endpoint

The primary efficacy endpoint for this study is the change in the TTS (of the YGTSS) from baseline to week 12.

[figure not shown]
9.5.2. Key Secondary Endpoints

Key secondary endpoints for this study are as follows:

1. Change in the TS-CGI score from baseline to week 12
2. Change in the TS-PGII score from baseline to week 12
3. Change in the C&A-GTS-QOL ADL subscale score from baseline to week 12

9.5.3. Exploratory Endpoints

Exploratory endpoints for this study are as follows:

9.5.4. Planned Method of Analysis

The mITT analysis set (see Section 9.2) will be used for all efficacy analyses. Summaries will be presented by treatment group.

9.5.4.1. Primary Efficacy Analysis

The primary analysis will be a mixed-model, repeated-measures with the change in the TTS as the dependent variable. The model will include fixed effects for treatment group, week (5 levels: weeks 2, 4, 6, 9, and 12), and the treatment group by week interaction. The baseline TTS, region, and age group at baseline (2 levels: 6 to 11 years, 12 to 16 years) will be included as covariates. The unstructured covariance matrix for repeated observations within patients will be used. In case that the model does not converge, the Maximum-Likelihood estimation method will be used instead of the default Restricted Maximum-Likelihood. If the model still does not converge, then a simpler covariance structure with fewer parameters will be used, according to the following order: Heterogeneous Autoregressive (1), Heterogeneous Compound Symmetry, Autoregressive (1), and Compound Symmetry. The least squares means of the change in TTS from baseline at week 12 will be compared (the active treatment arm and the placebo arm) using a 2-sided test at the alpha=0.05 level of significance.

In addition, actual values and changes in the TTS from baseline to each visit will be summarized using descriptive statistics.

9.5.4.2. Sensitivity Analysis

Sensitivity analyses for missing data, the statistical model, and the increase in sample size will be provided in the statistical analysis plan.

9.5.4.3. Key Secondary Efficacy Analyses

A hierarchical (fixed-sequence) testing approach will be used for the analysis of the primary and key secondary endpoints to maintain the experiment-wise type I error rate of 5%. If an endpoint is not statistically significant, confirmatory hypothesis testing will not be carried out on the remaining hypotheses, and remaining hypotheses will be considered exploratory rather than confirmatory. The change in the TS-CGI (1) and C&A-GTS-QOL ADL subscale (3) scores from baseline to week 12 will be summarized and analyzed in the same fashion as the primary analysis, with the exception that the baseline value of the given endpoint will be included as the covariate. TS-PGII (2) will be analyzed using a Cochran-Mantel-Haenszel row mean score test with a modified ridit scoring that controls for age group.

9.5.4.4. Exploratory Analyses

A 10x10 grid of black and white squares, likely a binary image or a mask. The pattern consists of a 3x3 block of black squares in the top-left, followed by a 2x2 block of white squares, and then a 5x5 block of black squares extending to the right and bottom. The bottom-right square is white.

9.6. Multiple Comparisons and Multiplicity

The hierarchical testing method will be used to maintain the experiment-wise type I error of 5% level for the primary and key secondary analyses. The primary efficacy endpoint will first be tested at the 5% type I error level. If the p-value of the primary analysis is ≤ 0.05 , the secondary hypotheses will be tested in the order listed for the secondary endpoints (Section 9.5.2) until either an analysis produces a p-value > 0.05 or all analyses result in a p-value ≤ 0.05 .

9.7. Safety Endpoints and Analysis

Safety analyses will be performed on the safety analysis set.

9.7.1. Safety Endpoints

Safety endpoints for this study are as follows:

- incidence of adverse events
- observed values and changes from baseline in vital signs
- observed values and change from baseline in the CDI-2 (Parent and Self-report versions)
- observed values in the C-SSRS
- observed values in ECG parameters and shifts from screening for clinically significant abnormal findings
- observed values and changes from screening in clinical laboratory parameters (hematology, chemistry, and urinalysis)

9.7.2. Safety Analysis

All adverse events will be coded using the Medical Dictionary for Regulatory Activities. Each patient will be counted only once in each preferred term or system organ class category for the analyses of safety. Summaries will be presented for all adverse events, adverse events determined by the investigator to be related to study treatment, serious adverse events, and adverse events causing withdrawal from the study. Summaries will be presented by treatment group and for all patients. Patient listings of serious adverse events and adverse events leading to withdrawal will be presented.

Observed values and changes from baseline in laboratory results and vital signs will be summarized descriptively.

Observed values in ECG parameters will be summarized, and counts and percentages of abnormal findings will be presented. In addition, the number and percentage of patients with on-treatment QTcF values > 450 , > 480 , or > 500 msec and change from baseline > 30 or > 60 msec will be presented.

The use of concomitant medications will be summarized by therapeutic class using descriptive statistics. Concomitant medications will include all medications taken while the patient is treated with IMP.

Observed values in the C-SSRS and observed values and changes from baseline in the CDI-2 (Parent and Self-report versions) will be presented by treatment group for all patients.

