Note: Use of topiramate (up to 200 mg/day) is allowed if dosing has been stable for at least 4 weeks before screening.

- Note: Use of guanfacine or clonidine is allowed regardless of indication (ie, if prescribed for tics or Tourette syndrome) if the dosing has been stable for at least

4 weeks before screening and no changes to dose or frequency are anticipated during the course of the study. If discontinuation of either medication is anticipated due to ineffectiveness, poor tolerability, or patient/caregiver preference, discontinuation should occur 4 or more weeks prior to the screening visit.

- k. Patient has received treatment with deep brain stimulation, transmagnetic stimulation, or transcranial direct current stimulation for reduction of tics within 4 weeks of the screening visit.
- l. Patient has an unstable or serious medical illness at screening or baseline
- m. Patient has a QT interval corrected for heart rate using Fridericia's formula (QTcF) interval value >450 msec (males) or >460 msec (females) or >480 msec (with right bundle branch block) on 12-lead ECG at screening, OR requires treatment with drugs known to prolong the QT interval (see Appendix A, [Table 6](#) for a complete list of prohibited QT-prolonging drugs).
- n. Patients with a history of torsade de pointes, congenital long QT syndrome, bradyarrhythmias, or uncompensated heart failure.
- o. Patient has evidence of hepatic impairment, as indicated by:
 - aspartate aminotransferase (AST) or alanine aminotransferase (ALT) $>2.5 \times$ the upper limit of the normal range (ULN) at screening
 - alkaline phosphatase (ALP) or total bilirubin (Tbil) $>2 \times$ ULN at screening

Note: Patients with Gilbert's Syndrome are eligible to participate, if approved by the medical monitor.

Note: Patients with abnormalities in 2 or more of the following clinical laboratory parameters must be approved for enrollment by the medical monitor: AST, ALT, ALP, and Tbil.

- p. Patient has evidence of clinically significant renal impairment, indicated by a serum creatinine $>1.5 \times$ ULN at screening.
- q. Patient has received a MAOI within 14 days of the baseline visit.
- r. Patient has a known allergy to any of the components of the IMP.
- s. Patient has participated in an investigational drug or device study and received IMP/intervention within 30 days or 5 drug half-lives of baseline, whichever is longer.

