**Table 5: Criteria for Markedly Abnormal Vital Sign Parameters by Age**

Parameter (unit)	Age (years old)	Markedly Low	Markedly High
SBP (supine, standing) (mmHg)	6-12	Value $\leq$ 70 and $\geq$ 20 decrease from baseline	Value $\geq$ 120 and $\geq$ 20 increase from baseline
	13-18	Value $\leq$ 90 and $\geq$ 20 decrease from baseline	Value $\geq$ 135 and $\geq$ 20 increase from baseline
DBP (supine, standing) (mmHg)	6-12	Value $\leq$ 40 and $\geq$ 15 decrease from baseline	Value $\geq$ 80 and $\geq$ 15 increase from baseline
	13-18	Value $\leq$ 50 and $\geq$ 15 decrease from baseline	Value $\geq$ 90 and $\geq$ 15 increase from baseline
Pulse rate (supine, standing) (bpm)	6-10	Value $\leq$ 60 and $\geq$ 15 decrease from baseline	Value $\geq$ 135 and $\geq$ 15 increase from baseline
	11-18	Value $\leq$ 50 and $\geq$ 15 decrease from baseline	Value $\geq$ 120 and $\geq$ 15 increase from baseline
SBP orthostatic criteria (mmHg)	~	$\geq$ 20 decrease from supine to standing position	NA
DBP orthostatic criteria (mmHg)	~	$\geq$ 10 decrease from supine to standing position	NA
Pulse rate orthostatic criteria (bpm)	~	NA	$\geq$ 20 increase from supine to standing position
Temperature (°C)	~	NA	Value $\geq$ 38.3°C and $\geq$ 0.8°C increase from baseline

Note: ~ means that the abnormal range is applicable for all patients within age group: 6 to 17 years old.

Vital signs data will be provided in a data listing.

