## 9.9. ECG

Assessment of Standard 12-lead ECG are obtained at screening, baseline, weeks 4, 6, and 12. A central ECG Standard 12-lead ECG will record heart rate (HR), PR interval, RR interval, QT interval, Frederica's corrected QT interval (QTcF), and QRS duration. The overall ECG assessment will be centrally reported as "Normal" or "Abnormal" with respect to relevant abnormalities. If a post-baseline QTcF value  $>500$  msec or change from baseline  $>60$  msec is found, the investigator should repeat the ECG assessment twice. In this case, the confirmed QTcF, defined as the average of all 3 ECG values at the visit, will be used for summary. If ECG tests are repeated on the same day for any other reason per investigators discretion, the average of all ECG values on that day will be used for summary.

Observed results of each ECG parameter and change from baseline will be summarized by treatment and overall, and by visit using descriptive statistics.

In addition, for QTcF, average baseline confirmed QTcF (the average of the screening and Day 1 QTcF), and the change from average baseline will be summarized by treatment and overall, and by visit using descriptive statistics.

QTcF values will be classified as having QTc prolongation according to the following conditions.

QTc Prolongation
Confirmed QTcF $>450$ msec
Confirmed QTcF $>480$ msec
Confirmed QTcF $>500$ msec
Increase from baseline QTcF $\geq 60$ msec
Increase from average baseline confirmed QTcF $\geq 60$ msec
Increase from baseline QTcF $\geq 30$ msec
Increase from average baseline confirmed QTcF $\geq 30$ msec

The number and percentage of patients with QTc prolongation will be summarized by treatment and overall, and by visit.

A shift table comparing the overall ECG assessment from baseline to end of treatment will be presented.

In addition, the abnormal post-baseline ECG results will also be summarized for patients with at least one abnormal value during the treatment period. The summary will be completed by treatment and overall, and age groups (6 - < 8 years, 8 - < 12 years, and 12 - < 16 years), and overall using the age at the time of the individual assessment.

Criteria for abnormal values used in the study are presented in [Table 6](#).

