**Table 6: Criteria for Abnormal ECG Parameters by Age**

ECG parameter (unit)	Age (years old)	Abnormally Low	Abnormally High
HR (bpm)	6 to <8	< 65	> 115
	8 to <12	< 55	> 110
	12 to <16	< 50	> 105
	≥16	< 50	> 100
PR interval (msec)	6 to <8	--	> 160
	8 to <12	--	> 175
	12 to <16	--	> 180
	≥16	--	> 200
QRS interval (msec)	6 to <8	--	> 100
	8 to <12	--	> 105
	12 to <16	--	> 110
	≥16	--	> 120

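### Counts of on-treatment QTcF above 450 msec and of abnormal heart rate, PR or QRS include values already beyond the limit before dosing

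*Protocol*

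**What the plan says.** **Absolute counts.** Protocol section 9.7.2 plans "the number and percentage of patients with on-treatment QTcF values" above 450, 480 or 500 msec and, for ECG findings generally, says "counts and percentages of abnormal findings will be presented". SAP section 9.9 lists the three confirmed-QTcF thresholds under the label QTc prolongation: "The number and percentage of patients with QTc prolongation will be summarized by treatment and overall, and by visit". Heart rate, PR and QRS are handled separately: "the abnormal post-baseline ECG results will also be summarized for patients with at least one abnormal value during the treatment period". The limits are in Table 6, "Criteria for Abnormal ECG Parameters by Age". They are age-banded absolute values with no change-from-baseline term.

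**Entry.** Criterion m (protocol section 4.2) excludes a QTcF above 450 msec in males, "or >460 msec (females) or >480 msec (with right bundle branch block) on 12-lead ECG at screening". It applies to the screening ECG only and sets no heart rate, PR or QRS limit. A Day 1 ECG is also recorded (protocol section 3.4).

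**Baseline-referenced outputs.** SAP section 9.9 also gives:
- change from baseline for each ECG parameter;
- change from the average of the screening and Day 1 QTcF;
- QTcF increases of at least 30 and at least 60 msec from either baseline (the protocol says above 30 or 60);
- a baseline to end-of-treatment shift table of the overall Normal/Abnormal reading.

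**The rule for vital signs.** Table 5 of the SAP requires a limit and a change together for blood pressure, pulse and temperature, for example "Value $\geq$ 120 and $\geq$ 20 increase from baseline". Its orthostatic rows have no such condition.

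**The concern.** A count headed as on-treatment abnormality is normally read as something that arose on treatment. Here a girl who enters at 455 msec and stays there is tabulated under QTc prolongation. A child whose PR or QRS already exceeded the age limit at screening is tabulated as abnormal during treatment. The SAP avoids this for most vital signs through Table 5, and for adverse events by tabulating only those that begin or worsen after the first dose (SAP section 9.4). The ECG limits have no matching rule.

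At stake is how the ECG tables read. If pre-existing cases occur in both arms, both rates are too high as estimates of new abnormality and the ratio between them moves toward 1. If there are only a few and they fall unevenly, they can create or hide a difference that has nothing to do with the drug.

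**Working it through.** The documents give no ECG rate, so there is no planned figure to reproduce. The check has four steps.

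**1. Which rows can contain pre-existing cases?**
- QTcF above 450 msec: yes. Criterion m allows females above 450 and up to 460 msec, and right bundle branch block up to 480 msec.
- QTcF above 480 or 500 msec: not through entry at screening. Only a value that rose between screening and Day 1 could pre-exist.
- Heart rate, PR and QRS: yes. Entry sets no limit on them.

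**2. Do the other outputs show who newly crossed a limit?**
- Mean change per parameter describes the group and does not identify patients crossing a limit.
- The 30 and 60 msec rows cover QTcF only. They do not say whether a threshold was crossed.
- The shift table covers only the overall reading, and only to end of treatment. It shows no QTcF category, heart rate, PR or QRS, and a week 4 or 6 abnormality that has resolved by then would not appear.

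**3. How much could it matter?** Let b be the share of patients with a persisting pre-existing abnormality, equal in both arms, and p the new-onset rate among the rest. The observed rate is b + (1 − b)p, so the risk difference is (1 − b)(pA − pP). Assume new-onset rates of 10% on active and 2% on placebo, and b from 1% to 20%. None of these is in the documents. Arm size is 58 (protocol section 9.1).

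| b | Pre-existing per 58 | Observed rates | Risk difference (points) | Risk ratio |
|---|---|---|---|---|
| 0 | 0 | 10.0% v 2.0% | 8.0 | 5.00 |
| 1% | 0.6 | 10.9% v 3.0% | 7.9 | 3.66 |
| 5% | 2.9 | 14.5% v 6.9% | 7.6 | 2.10 |
| 10% | 5.8 | 19.0% v 11.8% | 7.2 | 1.61 |
| 20% | 11.6 | 28.0% v 21.6% | 6.4 | 1.30 |

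For example, at b = 5% the rates are 0.05 + 0.95 × 0.10 = 0.145 and 0.05 + 0.95 × 0.02 = 0.069, with ratio 2.10. The risk difference falls only by the factor (1 − b); the ratio falls much faster.

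**4. What b is plausible, and is equal b realistic?** For QTcF above 450 msec, assume a normal distribution in girls with mean m of 400 to 420 msec and SD s of 15 to 22 msec, truncated at the 460 msec entry limit. The share already above 450 is [Φ((460 − m)/s) − Φ((450 − m)/s)] / Φ((460 − m)/s). This runs from 0.04% (m = 400, s = 15) to 5.4% (m = 420, s = 22). If 25% of 116 patients are girls (29, assumed), that is about 0 to 1.6 patients in the whole trial, plus any with right bundle branch block. No similar estimate is possible for Table 6 items.

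With counts this small, b need not be equal across arms. If 4 of 116 patients are pre-existing cases, the chance of an exact 2:2 split is C(58,2)² / C(116,4) = 2,732,409 / 7,160,245 = 0.38. The arms then differ by 2 or more with probability 62%, and placebo has the larger number with probability 31%.

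**The case against.** The strongest reply is that the plan does not neglect the pre-treatment ECG. It summarises change from baseline for every parameter, uses two QTcF baselines, pairs the thresholds with change categories and includes a shift table. The stated endpoint is observed values and shifts from screening for clinically significant findings, so the disputed counts are supplementary and descriptive. All of that is correct. A reader might infer that ECG safety is analysed without reference to baseline; the SAP does not support that. What remains is the narrower gap in step 2. The SAP revision history also records that ECG clinical significance was dropped because it was not collected, so section 9.9 has no output on shifts in clinically significant findings.

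Other points stand in part:
- A reader might think the entry criteria also inflate the 480 msec row. They do not, because values above 480 msec are barred at screening even with right bundle branch block.
- Table 5 requires a pulse change of at least 15 bpm for its markedly abnormal limits, so heart rate is partly covered there. PR and QRS are not.
- The summary uses age at each assessment, so an unchanged heart rate of 112 bpm is within limits at age 7 (above 115 is abnormal) and abnormal at age 8 (above 110). This is an explicit SAP choice that can affect few children. Fixing age at baseline would be a preference, not a correction.
- The QTc table is by visit and the table shells are redacted, so a baseline column may exist. Separate counts at each visit would still not link a patient's baseline to the later value.
- Replacing the planned rows would lose information. A girl rising from 455 to 478 msec changes by 23 msec, below the 30 msec row, and would leave the 450 msec row too. This is a sound reason to add tables and keep the existing ones.

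**Conclusion.** The point holds for QTcF above 450 msec and for the Table 6 counts of heart rate, PR and QRS. Followed as written, the plan reports unchanged pre-existing values as on-treatment abnormalities, and no output described in the SAP text identifies new ones.

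Its size cannot be established from the documents. On the assumptions shown, it is probably small for QTcF above 450 msec (about 0 to 1.6 girls in the trial, plus any right bundle branch block). It is essentially absent for 480 and 500 msec and could be larger for Table 6 items. A reader might infer that a drug signal will be masked by a known amount. That is not supported: the prevalence is not given, the plan specifies no significance test on these counts, and with few cases the distortion can go in either direction. This is a reporting weakness that is easy to close; it does not invalidate the ECG safety analysis.

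**What to change.** Keep the planned absolute counts. Add to SAP section 9.9, with a matching line in protocol section 9.7.2:

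1. Treatment-emergent counts for each QTcF threshold and each Table 6 limit. Numerator and denominator are restricted to patients not beyond that limit at baseline (for low heart rate, not below it). Use the SAP section 6.2.1 baseline for heart rate, PR and QRS, and the screening/Day 1 average that section 9.9 already derives for QTcF.
2. Baseline-by-worst-on-treatment shift tables for QTcF category, heart rate, PR and QRS, by arm.

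Under the assumptions in the working, the restricted count returns the risk ratio of 5.00 at every b, on 58(1 − b) patients per arm: 57.4 at 1%, 55.1 at 5%, 52.2 at 10% and 46.4 at 20%. The cost is SAP and protocol wording, a few extra tables and slightly smaller denominators. All the ECGs needed are already collected.

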9.8. Pharmacokinetic Analysis

The pharmacokinetic endpoint is listed in Section [2.3.5](#). Samples collected for pharmacokinetic analysis will be quantified for α -HTBZ and β -HTBZ of TEV-50717, and other metabolites (as needed), will be analyzed using population pharmacokinetic techniques. Analysis methods will be detailed in a separate population pharmacokinetic analysis plan. Exploratory pharmacokinetic/PD analysis may be performed on PD/safety endpoints.

9.9. Planned Interim Analysis

No interim analysis is planned for this study.

9.10. Reporting Deviations from the Statistical Plan

Deviations from the statistical plan, along with the reasons for the deviations, will be described in protocol amendments, the statistical analysis plan, the clinical study report, or any combination of these, as appropriate, and in accordance with applicable national, local, and regional requirements and regulations.

10. DIRECT ACCESS TO SOURCE DATA AND DOCUMENTS

The medical experts, study monitors, auditors, IEC/IRB, and inspectors from competent authority (or their agents) will be given direct access to source data and documents (eg, medical charts/records, laboratory test results, printouts, videotapes) for source data verification, provided that patient confidentiality is maintained in accordance with national and local requirements.

The investigator must maintain the original records (ie, source documents) of each patient's data at all times. Examples of source documents are hospital records, office visit records, examining physician's finding or notes, consultant's written opinion or notes, laboratory reports, drug inventory, IMP label records, diary data, protocol-required worksheets, and CRFs that are used as the source (see Section 3.12).

The investigator will maintain a confidential patient identification list that allows the unambiguous identification of each patient. All study-related documents must be kept until notification by the sponsor.

11. QUALITY CONTROL AND QUALITY ASSURANCE

11.1. Protocol Amendments and Protocol Deviations and Violations

11.1.1. Protocol Amendments

No changes from the final approved (signed) protocol will be initiated without the prior written approval or favorable opinion of a written amendment by the IEC/IRB and national and local competent authorities, as applicable, except when necessary to address immediate safety concerns to the patients or when the change involves only nonsubstantial logistics or administration. The principal investigator at each investigational center, the coordinating investigator (if applicable), and the sponsor will sign the protocol amendment.

